1 BACKGROUND

Prostate cancer is the most common non-cutaneous cancer and among the top three causes of cancer deaths among men in Finland and other Western countries. Burden of health care costs due to the condition rise up to 180 million euros/year in Finland (1).

Androgens are vital for prostate cancer progression, and androgen deprivation therapy is cornerstone in management of advanced or recurrent prostate cancer that is beyond curative treatment. In androgen deprivation therapy (ADT) serum testosterone is lowered either medically or surgically to a level lower than 1,72 $\mu\text{mol/l}$ (50 ng/dl). (2) These prevents activation of androgen receptors in prostate cancer cells, leading to involution of the prostate tumor and metastases, decreased proliferation and increased apoptosis of prostate cancer cells (3,4).

Common side effects of ADT include fatigue, weight gain, muscle loss, decreased libido and erectile dysfunction, amounting to decreased quality of life (5). Low serum testosterone has also been linked with increased risk for type II diabetes and metabolic syndrome (6). Also associations with elevated risk for memory impairment and cardiovascular disease have been proposed (7,8).

Systematic review published in 2012 found strong evidence for improved overall quality of life among ADT-treated prostate cancer patients participating in supervised resistance training. Moderate evidence was found also for improved physical and social well-being. The authors recommended exercise for all prostate cancer patients on ADT and called for further studies comparing supervised and unsupervised exercise (9). A recent randomized trial found equal fatigue reduction and vitality increase both with supervised and unsupervised exercise (10).

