3 STUDY SETTING

This is a randomized, controlled clinical trial. The study aims to recruit 40 men on ADT for prostate cancer. This will be a pilot study to estimate effect sizes in Finnish population to inform further larger trial. For this reason the sample size will be smaller compared to previous studies on the topic (10,11) and no power calculation is performed yet.

Figure: Study flow chart

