4 INCLUSION- AND EXCLUSION CRITERIA

Inclusion criteria:

- ADT for prostate cancer, regardless of treatment duration
- Willingness to participate in the study; signing of informed consent

Exclusion criteria:

- Unability for physical exertion; ECOG 2 or higher
- High risk for bone fractures as evaluated by the attending clinician
- Non-Finnish speaking; inability to comprehend Finnish

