5 INTERVENTION

All participants attend introductory lecture, where a urologist informs them about adverse effects of ADT and positive effects of exercise during ADT, exercise instructor gives advice for training both at home and in the gym and nutritional therapist tells about nutrition to overcome adverse effects of ADT and support training.

After the introductory lecture the participants are randomized 1:1 to either the supervised or non-supervised exercise group (Figure). Men in the supervised group participate in progressive group exercise sessions twice a week for total of 12 weeks at the Varala sports academy in Tampere, Finland. Each exercise session includes both aerobic and resistance training targeting all major muscle groups (Additional document I, exercise program). The non-supervised group will exercise independently for 12 weeks according to the instructions given at the introductory lecture. The first control visit will be after this first period of 12 weeks of exercise.

After the first follow-up visit both groups will continue non-supervised exercise for 12 weeks, after which the second control visit will be arranged. Special focus on the second control visit is to see how many in each group has been able to carry on active exercising, i.e. has the intervention promoted long-term change in exercise activity.

Both study groups will be given Polar wrist activity monitors to be used 24 h/day for the entire course of the study.

All participants are asked to fill validated quality of life surveys EORTC QLQC-30 (overall quality of life) and EORTC QLQC-PR25 (prostate cancer-specific quality of life) at baseline and again at 1st and 2nd control visits. Plasma lipid and glucose parameters, blood pressure and body composition will be measured at each of these visits.

At each visit a separate blood sample is taken and stored for future measurement of biomarkers associated with prostate cancer progression, glucose and lipid metabolism and effects of exercise.

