Of the secondary outcomes median time to castration resistance and death are compared between the trial arms using Kaplan-Meier analysis and log-rank test. Analysis for risks of castration resistance, death, prostate cancer death, cardiovascular disease, bone fracture and memory impairment will be analysed using Cox regression with months from the study randomization as the time metric. The regression model will be adjusted for the study arm, age at baseline, time between prostate cancer diagnosis and randomization, ADT method and the time on ADT before participating in the trial.

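### The Cox models and log-rank tests for castration resistance and death ignore metastatic status, so a chance imbalance among 40 men carries straight into the estimated effect of supervision

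*Combined protocol and SAP*

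**What the plan says.** Section 3 sets the size and purpose: "The study aims to recruit 40 men on ADT for prostate cancer", and "This will be a pilot study to estimate effect sizes in Finnish population to inform further larger trial". It adds that "no power calculation is performed yet".

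Section 4 admits men on this criterion: "ADT for prostate cancer, regardless of treatment duration". No criterion refers to stage or metastases. Section 1 describes the treated population as mixed: "androgen deprivation therapy is cornerstone in management of advanced or recurrent prostate cancer that is beyond curative treatment". Section 5 says that "the participants are randomized 1:1 to either the supervised or non-supervised exercise group" and mentions no stratification factor.

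Section 7 (Statistical analysis) compares time to castration resistance and time to death by Kaplan-Meier curves and log-rank tests, with no strata. It then plans Cox regression for castration resistance, death, prostate cancer death, cardiovascular disease, fracture and memory impairment. One covariate set serves all six: "The regression model will be adjusted for the study arm, age at baseline, time between prostate cancer diagnosis and randomization, ADT method", the list ending with "ADT method and the time on ADT before participating in the trial". Disease extent is not in it.

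**The concern.** Disease extent is likely to be a main driver of castration resistance, prostate cancer death and death. In the available text it is not controlled at entry, at allocation or in the analysis. In a trial of 40, an imbalance of several metastatic men between arms is an ordinary event, and the hazard ratio for supervision then partly reflects who was allocated where.

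What is at stake is the estimate. The pilot exists to supply effect sizes for a larger trial, and section 2 expects a lower risk of death with supervision. A displaced hazard ratio could be carried forward as if it were information about supervision.

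**Working it through.** The plan gives no event count, effect size or power for these outcomes, so there is no figure of its own to reproduce.

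**Inputs from the documents:** 40 men, 1:1 allocation (20 per arm), five model terms.

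**Assumed inputs:** 20–50% of men metastatic (8 to 20 of 40); metastatic hazard ratio (HR) 2 to 5; in the simulations that use 20 of 40 metastatic, baseline hazard 0.12 per year and 5 years of follow-up, giving 19–28 events.

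**Step 1: how often imbalance occurs.** With M metastatic men among 40, the number k allocated to one arm has probability C(M,k)·C(40−M,20−k)/C(40,20), and the arms differ by |2k−M|. For M = 8, a difference of 4 or more means k ≤ 2 or k ≥ 6:

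2 × (225,792,840 + 2,778,988,800 + 13,200,196,800) / 137,846,528,820 = 0.235.

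| Metastatic men of 40 | Differ by ≥4 | Differ by ≥6 |
|---|---|---|
| 8 (20%) | 0.235 | 0.044 |
| 12 (30%) | 0.301 | 0.082 |
| 16 (40%) | 0.333 | 0.105 |
| 20 (50%) | 0.343 | 0.113 |

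**Step 2: rough size by hand.** With no true effect, and a and b metastatic men in the two arms, the ratio of average hazards at the start of follow-up is (a·HR + 20 − a)/(b·HR + 20 − b).

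- 12 v 8 men: 32/28 = 1.14 (HR 2), 44/36 = 1.22 (HR 3), 68/52 = 1.31 (HR 5).
- 10 v 6 men: 30/26 = 1.15, 40/32 = 1.25, 60/44 = 1.36.
- 6 v 2 men: 26/22 = 1.18, 32/24 = 1.33, 44/28 = 1.57.

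This ignores changes in the risk set over time and the other covariates, but shows where the shift comes from. At a lower metastatic share, a 4-man difference is rarer but not smaller in effect.

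**Step 3: the planned five-term model, simulated with no true effect.** Median hazard ratio for the arm with more metastatic men, over metastatic HR 2–5:

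| Setting | 4-man difference | 6-man difference | With metastatic status in the model |
|---|---|---|---|
| 20 of 40 metastatic; time variables unrelated to metastatic status | 1.15–1.37 | 1.22–1.60 | 0.98–1.01 |
| 20 of 40; ADT starts at diagnosis in 70–90% of metastatic and 10–30% of other men | 1.13–1.33 | – | – |
| 16 of 40; time since diagnosis linked to metastatic status | 1.17–1.32 | 1.20–1.41 (HR 2–3) | 0.95–1.03 |

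The planned covariates do not absorb the imbalance, even where the two time variables carry some information on disease extent. In the last row, metastatic status entered as a covariate or as a stratum.

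**Step 4: averaged over all allocations.** In arm-only null simulations (16 of 40 metastatic, 20 or 32 events, about 4,000 replicates per setting), two-sided type I error was 4–5% without metastatic status and 5–6% with it.

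**Step 5: attenuation and power, true HR 0.50.** In the second setting of step 3, the planned model's median was 0.47–0.49 at metastatic HR 2–3 and 0.53–0.56 at HR 5. Power for the planned model, against one with metastatic status in place of time since diagnosis, was 28–29% v 29% (HR 2), 32–33% v 36–37% (HR 3) and 23–29% v 37–39% (HR 5).

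**Step 6: scale.** Schoenfeld's formula gives power Φ(√D·|ln HR|/2 − 1.96). With all 40 men having an event and HR 0.5: Φ(6.325 × 0.693/2 − 1.96) = Φ(0.23) = 59%. For 80% power, D = 4 × (1.96 + 0.842)²/0.693² ≈ 65.3, so 66 events.

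**The case against.** The strongest reply is that randomisation already deals with this. Imbalance is chance, not bias; type I error over all allocations is nominal; and the confidence interval allows for it. That is correct as far as it goes. The shift at a 4-man difference is ln 1.15 = 0.14 to ln 1.35 = 0.30, against a standard error of about 2/√D, which is 0.38–0.46 for 28 to 19 events. So it is roughly 0.3 to 0.8 of a standard error. But once the allocation is known the displacement is known in direction and largely removable, and an estimate intended for planning should not carry it.

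A reader might also infer three stronger things that the documents do not support:

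- **That a real effect is generally pulled towards 1.** Step 5 shows no attenuation in the planned model at metastatic HR 2–3. It appears only near HR 5, and the same holds for any sizeable power loss.
- **That the two time variables are redundant, so one can be dropped.** They coincide only for men who start ADT at diagnosis. Section 1 also names recurrent disease, where time since diagnosis includes a period before ADT. With 30–90% starting ADT at diagnosis (assumed), the correlation is about 0.62–0.86 (variance inflation 1.6–3.9), which is moderate.
- **That all six Cox models are affected alike.** The argument is made for castration resistance and the two death outcomes. It has not been made for cardiovascular disease, fracture or memory impairment.

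Two further limits stand. The metastatic share is unknown, and excluding men with ECOG 2 or higher or high fracture risk may lower it; at 4 of 40, a difference of 4 occurs in 11% of randomisations and one of 6 cannot occur. These are also long-term outcomes of a pilot, not its primary outcomes, and power is low either way.

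**Conclusion.** The point holds for castration resistance, prostate cancer death and death. Under the assumed 20–50% metastatic, a difference of 4 or more men arises in 24–34% of randomisations and one of 6 or more in 4–11%. A 4-man difference moves a null hazard ratio to about 1.15–1.35, or its reciprocal, for a metastatic HR of 2–5; accounting for metastatic status brings it back to about 1.0. The simulated range rests on 40–50% metastatic.

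This is a conditional error in the estimate. It is not a systematic bias, an inflated overall type I error or a general attenuation. Share metastatic, its hazard ratio, event rate and follow-up are all assumptions. The flow chart and some pages were not available, so a stratification factor stated only there cannot be excluded. It is a cheap improvement, with no bearing on the primary outcomes.

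**What to change.** In section 7, for castration resistance, prostate cancer death and death only, state that the Cox models, and the log-rank tests for castration resistance and death, are stratified by metastatic status at randomisation (yes/no). Abstract it from the patient files already used for follow-up, and fix it before outcomes are examined. Keep the existing covariates: stratifying adds no coefficient, which matters when 20 events over five terms leave 20/5 = 4 events per term. Leave the cardiovascular, fracture and memory-impairment models as planned.

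The cost is one abstracted item per man, a sentence in the plan, and a slight loss of information from stratifying with few events.

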8 ETHICAL CONSIDERATIONS

8.1 BENEFITS AND RISK OF HARM FOR THE PARTICIPANTS

Evidence for quality of life improvement due to exercise is strong, and therefore the participants likely benefit from the study participation in both study arms. Participating in an exercise program increases risk of musculoskeletal injuries and possibly cardiovascular events. Such risks are minimized by selecting participants with adequate physical condition and tailoring the research program according to individual performance level.

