7 STUDY OUTCOMES AND STATISTICAL ANALYSIS

Primary outcomes:

- Daily total activity, measured during the entire course of study with wrist activity monitor in metabolic equivalents of task (MET) units
- Fasting plasma cholesterol, LDL, HDL and triglycerides, measured at baseline and again at the 1st and 2nd control visits
- Fasting plasma glucose and glycated haemoglobin (HbA1C), measured at baseline and again at the 1st and 2nd control visits
- Overall quality of life and prostate cancer-specific quality of life, measured with validated Finnish versions of EORTC QLQ-C30 v.3.0 ja EORTC QLQ-PR25 at baseline and at each control visit

Secondary outcomes:

- Change in daily activity after the end of supervised group exercise intervention; difference compared to the non-supervised group. Measured with wrist activity monitor in MET units
- Body mass composition, bioimpedance-based measurement of lean body mass, fat mass and skeletal mass as percentage of total body mass measured with TANITA MC-780 device

- Blood pressure level, measured at baseline and each control visit
- Subjective effect of exercise on quality of life and perceived adverse effects of ADT, as based on qualitative interviews

Long-term follow-up

The participants are followed via patient files and national health care registries. Outcomes to be followed are:

- Time from baseline to castration resistance (progression of prostate cancer despite ADT as evidenced by constantly rising PSA or radiological disease progression)
- Bone fractures
- Diagnosis of memory impairment
- Diagnosis of diabetes mellitus
- Diagnosis of cardiovascular disease
- Prostate cancer death
- Death due to any cause

Statistical analysis

All comparisons are done between the supervised and non-supervised exercise arms. Medians of daily activity (in MET units) and quantitative quality of life (as points from the EORTC surveys) at baseline and at each control visit are compared with either Mann-Whitney U-test or Student's t-test depending on normality of the data distribution. Difference in medians of plasma lipid parameters and glucose parameters are analyzed similarly.

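### No collection of musculoskeletal injuries or adverse events is described for the 24 weeks, although section 8.1 names injury and possible cardiovascular events as risks of the exercise

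*Combined protocol and SAP*

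**What the plan says.** Section 8.1 names the harms: "Participating in an exercise program increases risk of musculoskeletal injuries and possibly cardiovascular events". Its response is preventive: "Such risks are minimized by selecting participants with adequate physical condition and tailoring the research program according to individual performance level". It says nothing about recording or reporting such events.

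Section 7 lists no injury, fall or cardiovascular event among the primary or secondary outcomes. The one item there that mentions adverse effects concerns those of ADT and rests on qualitative interviews. Bone fractures and cardiovascular diagnoses appear under long-term follow-up, for which "The participants are followed via patient files and national health care registries". The analysis text in section 7 compares both between arms by Cox regression timed from randomization, with study arm as a model term. Section 2 also counts fracture risk among the secondary aims.

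Section 5 sets the contact pattern: "Men in the supervised group participate in progressive group exercise sessions twice a week for total of 12 weeks". The other arm trains alone over the same period, and both arms train unsupervised for a further 12 weeks. The visit content in section 5 is questionnaires, laboratory values, blood pressure, body composition and stored blood. The interview topics in section 6 cover ADT side effects, quality of life and obstacles to exercise. Neither section includes a question on harm from the exercise.

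**The concern.** The harm that section 8.1 states without qualification, musculoskeletal injury, has no described source of data unless it is a fracture. Sprains, strains and falls without fracture would go unrecorded. This is information that is never gathered, not an analysis detail left unwritten. Analysts cannot restore it later, and registries are unlikely to hold minor injuries in full.

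Section 3 presents the trial as a pilot to inform a larger one. An injury rate under supervised and unsupervised exercise is a natural input to that trial, and this plan would not supply it. Staff also see one arm far more often than the other in weeks 1-12. If injuries were later reported from what staff happened to notice, the supervised arm would tend to look worse for that reason alone.

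**Working it through.** The documents give no harm rate, power or significance level (section 3: "no power calculation is performed yet"), so there is no figure of the plan's own to reproduce. The main check is a reading of what is collected. The arithmetic shows what collection could achieve.

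**1. Harm against data source**

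| Harm | 24-week outcome or visit question | Long-term follow-up |
|---|---|---|
| Musculoskeletal injury other than fracture | None described | None described |
| Fracture | None described | Yes, both arms, from randomization |
| Cardiovascular event | None described | As a diagnosis, both arms, from randomization |

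The registry clock starts at randomization, so the 12 + 12 = 24 weeks fall within it. No separate table for those weeks is planned. A diagnosis outcome may also miss an acute or recurrent event in a man already diagnosed.

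**2. Scheduled contact in weeks 1-12 (section 5)**

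Supervised arm: 2 sessions x 12 weeks = 24. Non-supervised arm: no scheduled session before the first control visit.

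**3. What about 20 men per arm can show**

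Section 3: "The study aims to recruit 40 men on ADT for prostate cancer". Section 5: "the participants are randomized 1:1 to either the supervised or non-supervised exercise group". So 40 / 2 = 20 per arm, assuming no dropout.

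- Chance of seeing at least one event in an arm at an assumed true rate of 10%, if every man is asked: 1 - 0.9^20 = 0.878.
- Upper 95% limit for 0 of 20, one-sided: 1 - 0.05^(1/20) = 13.9%. Two-sided: 1 - 0.025^(1/20) = 16.8%.
- Approximate 95% half-width for a difference at equal rates p: 1.96 x sqrt(2p(1 - p)/20). For p = 10%, 20% and 30% this is 18.6, 24.8 and 28.4 percentage points.
- Power of Fisher's exact test at an assumed two-sided 0.05: 7% for 10% versus 20%, and 24% for 10% versus 30%.

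**4. Cardiovascular events in 24 weeks**

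At an assumed annual rate a, the expected number among 40 men is 40 x (1 - exp(-a x 24/52)). For a = 2% to 10% this gives about 0.4 to 1.8 events. The chance of none, exp(-40 x a x 24/52), runs from 69% to 16%.

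**5. Illustration of unequal noticing (all inputs assumed)**

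Take a true injury risk of 20% in both arms and 90% of injuries noticed in the supervised arm: 20 x 0.20 x 0.90 = 3.6 men. If 70%, 50% or 30% are noticed in the other arm, the counts there are 2.8, 2.0 or 1.2. The apparent risk ratios are 0.90/0.70 = 1.3, 0.90/0.50 = 1.8 and 0.90/0.30 = 3.0. These show the direction and how the effect scales. They do not estimate anything in this trial.

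**The case against.** A reader might infer that harms cannot be compared between the arms at all. The documents do not support that. Fractures and cardiovascular diagnoses come from the same sources in both arms, do not depend on session staff, are timed from randomization and are modelled with study arm. The intervention weeks are covered, and events in them could be extracted. This part of the objection stands and limits the point to injuries other than fractures, to the absence of adverse-event recording, and to the missing 24-week table.

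A reader might also infer that the design produces a harm comparison biased against supervision. That too goes beyond the text. No comparison of spontaneous reports is planned, so the bias would arise only if someone made one, and its size is unknown. The interviews reduce the imbalance somewhat: men in the non-supervised arm are asked how they managed the program and its obstacles, so a limiting injury might surface. They are not a structured harm question, however.

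The sentence in section 8.1 about minimising risk is a prospective ethical justification, in line with the exclusions in section 4. It is not a result that the trial undertakes to show, and failing to test it is no fault.

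Finally, 40 men cannot support a powered harm comparison even with complete data. That stands, and it is why the proposed outcome is descriptive.

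**Conclusion.** The point holds in a limited form. For the 24 weeks, the available text describes no collection of musculoskeletal injuries or adverse events, although the protocol itself names injury and possibly cardiovascular events as risks of exercise. Fractures and cardiovascular diagnoses are captured in both arms through patient files and registries, without a planned 24-week tabulation. The 24-to-0 difference in scheduled sessions gives a reason to collect harms symmetrically. It does not show that any planned analysis is biased.

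What is lost is a by-arm description of injury and a rate for the larger trial. The precision on offer is modest: 0 of 20 would still be compatible with a true rate up to 13.9% (one-sided) or 16.8% (two-sided). This rests on 20 men per arm with no dropout. It also rests on the text available to this review: some pages, including a stretch between section 8.2 and the references, could not be read, and safety provisions there cannot be ruled out. The change is worth making, but the gap does not affect the primary comparisons.

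**What to change.** Add one descriptive secondary outcome to section 7: the number and proportion of men per arm with a musculoskeletal injury, fall, fracture or cardiovascular event.

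- Put identical structured questions to every man at the first and second control visits. Ask the same questions at withdrawal of men who leave early; otherwise a man injured in a session who drops out before the visit would be missing from the comparison.
- Report counts and proportions by arm with exact confidence intervals and no hypothesis test.
- List events observed by session staff separately, outside the between-arm comparison.
- Tabulate fractures and cardiovascular diagnoses from registries or patient files in the first 24 weeks by arm.

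The cost is a short checklist at two visits that already take place, a brief contact at withdrawal, one line in the outcome list and one extra table. The drawbacks are recall over up to 12 weeks and wide intervals.

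### Cardiovascular events are named as a possible risk of exercise, but the eligibility criteria screen on function only and include no exclusion for cardiovascular contraindication

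*Combined protocol and SAP*

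**What the plan says.** Section 8.1 (benefits and risk of harm) states the hazard: "Participating in an exercise program increases risk of musculoskeletal injuries and possibly cardiovascular events". It then gives two safeguards in one sentence: "Such risks are minimized by selecting participants with adequate physical condition and tailoring the research program according to individual performance level".

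Section 4 (inclusion and exclusion criteria) is where selection is specified. There are two inclusion criteria: being on ADT for any length of time, and willingness to take part with signed consent. There are three exclusions:

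- "Unability for physical exertion; ECOG 2 or higher"
- "High risk for bone fractures as evaluated by the attending clinician"
- not speaking or understanding Finnish.

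Section 5 (intervention) describes what men do once enrolled. All attend an introductory lecture at which, among other things, an "exercise instructor gives advice for training both at home and in the gym". They are then randomised. "Men in the supervised group participate in progressive group exercise sessions twice a week for total of 12 weeks"; the other arm exercises independently over the same period. For the supervised arm, "Each exercise session includes both aerobic and resistance training targeting all major muscle groups (Additional document I, exercise program").

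**The concern.** The safeguard in section 8.1 has to be delivered by the criteria in section 4. The hazard named is partly cardiovascular, but the matching criterion asks how well a man functions. Function and contraindication are different things: a man may be active and symptom-free in daily life and still have a cardiac condition for which his clinician would advise against training.

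The protocol does not rely on function alone for fracture risk. It adds a separate exclusion and says who judges it. The cardiovascular hazard has no such counterpart.

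What is at stake is participant safety at entry and consistent handling of eligibility. One clinician might exclude such a man under the first criterion while another, reading the same words, enrols him. No estimate or test in section 7 depends on this. However, section 3 describes the trial as a pilot for a larger one, so the eligibility wording may be carried forward.

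**Working it through.** The plan gives no figure to reproduce here. The check is whether the criteria deliver what section 8.1 says they deliver.

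**Step 1. The hazards named.** Section 8.1 names two: musculoskeletal injury and, possibly, cardiovascular events. Section 1 also notes proposed links between low testosterone and cardiovascular disease, and section 7 follows cardiovascular diagnoses over the long term. The authors treat the risk as relevant to these men.

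**Step 2. Each criterion in section 4 against the cardiovascular hazard.**

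| Criterion | Basis | Judged by | Specific to cardiovascular contraindication? |
|---|---|---|---|
| Inclusion: on ADT | Treatment | Not stated | No |
| Inclusion: willing, consent signed | Consent | Participant | No |
| Exclusion: exertion / ECOG | Function | Not stated | No; overlaps where disease limits function |
| Exclusion: fracture risk | Specific hazard | Attending clinician | No |
| Exclusion: language | Communication | Not stated | No |

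Count: 0 of 2 inclusion criteria and 0 of 3 exclusions are specific to cardiovascular contraindication. One of the 3 exclusions is specific to fracture risk and clinician-judged, and one is a general functional criterion.

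**Step 3. Apply the functional criterion to two men.**

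- Man A has heart disease that limits him to ECOG 2 or makes him unable to exert himself. He is excluded, so the criterion works for him.
- Man B is at ECOG 0 or 1 and able to exert himself, but has a cardiovascular contraindication. Read literally, neither half of the criterion applies, and he is eligible. Read broadly, with inability taken to include being medically unfit for exertion, he is excluded. The text does not say which reading is meant or who decides.

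**Step 4. Look for another gate in the available text.** Blood pressure is measured at baseline (sections 5 and 7), but as an outcome, with no entry limit attached. No medical clearance or cardiac assessment appears in the sections that could be read.

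**Step 5. Which arm is affected.** Eligibility is settled before the 1:1 allocation, so Man B may go to either arm. In one he enters progressive aerobic and resistance sessions; in the other he exercises independently. The gap is common to both.

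**Step 6. Size.** "The study aims to recruit 40 men on ADT for prostate cancer". Each man excluded by a new criterion is 1/40 = 2.5% of the target. The number of men like Man B would be 40 × (proportion at ECOG 0–1 with a contraindication). The documents give nothing from which to set that proportion, so no number is put on it.

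**The case against.** The strongest reply is that the first exclusion already covers this. It sets inability for exertion alongside the ECOG cut-off, and a clinician could reasonably apply it to a man who must not exert himself for cardiac reasons. Section 8.1 supports that intention, because it names cardiovascular events and says selection deals with them. A protocol may also name one hazard specifically and cover another through general fitness, so the fracture exclusion does not by itself prove an error. Much of this stands: cardiovascular risk is not left wholly unaddressed. What remains is that the wording permits two readings that differ on who may enter, and the literal one admits Man B.

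A second reply is that screening may be described in material that could not be read, namely the flow chart in section 3 and some removed pages. This also stands, and it limits how firmly absence can be claimed. Section 4 itself is visible, however, and contains no pointer to such a step.

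Two stronger readings are tempting, and the documents do not support them.

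- A reader might infer that the danger sits mainly in the non-supervised arm and gauge it by the share of the trial spent without supervision. That share describes supervision, not eligibility. The entry gap applies to both arms, and the protocol sets no amount of unsupervised exercise.
- A reader might infer that the promised tailoring fails for the non-supervised men. Section 8.1 does not say which activities its tailoring covers. It may mean only the structured sessions, whose sheets in section 10 leave loads and machine settings to be filled in for each man.

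**Conclusion.** The point holds as a limited one. Section 8.1 relies on selection to reduce a cardiovascular risk that it names, while section 4 selects on function. On a literal reading, a man at ECOG 0–1 with a cardiovascular contraindication to exercise is eligible for either arm. The contrast with the clinician-judged fracture exclusion shows that the protocol already has a suitable form of words and has not used it for this hazard.

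The conclusion rests on two assumptions: that the first exclusion is applied as written, without the broader interpretation, and that no cardiac screening is described in the material not available. If either fails, what remains is a matter of clarity.

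The number of men affected cannot be derived and could be zero. A reader might go further and infer that the trial is unsafe as designed. The documents do not support that, since the risk is recognised, a related exclusion exists and no event rate is given. No analysis, estimate or sample-size statement changes. This is a cheap safety improvement worth making.

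**What to change.** In section 4, extend the second exclusion. After the reference to bone fractures, and before the words assigning the judgement to the attending clinician, insert: *or cardiovascular contraindication to exercise*. Record the clinician's judgement on both parts for every man before randomisation. Mandate no test, and leave what counts as a contraindication to the clinician. If screening is already described in the flow chart or the pages not available, a cross-reference in section 4 is enough.

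The cost is one phrase and one tick-box, alongside a judgement that the attending clinician is already asked to make. No extra visit, test or staff is needed. The downside is that any man excluded reduces the pool by 2.5% of the 40-man target, which may slow recruitment slightly, and the findings would apply to a slightly narrower population.
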